1.1. Primary Objectives

The primary co-objectives are to determine the effect of eAT versus WWS on executive function (Behavior Rating Inventory of Executive Function [BRIEF2/P] Global Composite Score), and vigilance (Go-No-Go; GNG).

1.2. Secondary Objectives

To determine the effect of eAT versus WWS on sleep-disordered breathing (SDB) symptoms, and quality of life health care utilization (HCU). We will track and compare group changes in health care utilization: sick days/intercurrent illness, asthma exacerbations; prescriptions and over-the-counter medication use; ambulatory or hospital encounters. Exploratory outcomes include change in anthropometry and blood pressure.

To identify factors that moderate the response to surgery including age, socioeconomic status (SES), race, asthma/atopy, secondhand smoke exposure, short sleep duration and assessment of family function competency.

As an exploratory aim, to determine whether quantitative snoring metrics from the Tascon DR-10L Snoring Microphone correlate with the above outcomes.

As an exploratory aim, to determine whether participants would be willing to be contacted with long-term follow-up questions to assess the feasibility of conducting a study to evaluate the long-term outcomes in children with mild sleep disordered breathing, and to exam the number of children that sought additional treatment for sleep disordered breathing after their one-year participation period.

2. Study Design

2.1. General Design

This will be a randomized, single-blind 12-month intervention study that compares the impact of AT on measures of behavior, quality of life and HCU in children with MSDB. The proposed study will involve participation of children and their caregivers. Children with symptoms of MSDB will be recruited from each site's sleep clinics and laboratories, otolaryngology clinics, asthma clinics and general pediatric clinics. Potentially eligible children who are reported to be snorers at each site will be identified through systematic screening of health records and parent interviews. Children who meet study eligibility criteria will be randomized to having either eAT or WWSC for 12 months. In addition to the enrollment PSG at baseline, participants will receive behavioral testing, assessment of SDB symptoms, sleepiness, quality of life, anthropometry, and blood pressure. PSG and baseline measures will be repeated at 12-months. At 6 months caregivers will complete neurobehavioral assessments remotely, except for Virginia , where they will have an in person visit with child neuro behavior testing. Potential factors that may affect response to AT will also be assessed (asthma and atopy, secondhand smoke exposure, , family functioning). Approximately 920 participants will undergo baseline screening PSG, and 460 participants will be randomized. Both genders and all racial and ethnic groups will be eligible for participation. Participants failing baseline screening PSG will be referred for clinical care. It is anticipated that ~50% of participants will be eligible after PSG.460 eligible children, 230 per treatment arm, will be randomized to one of two treatment groups, and followed for a 12-month period.

Eligible participants will be randomized to one of two management groups:

[figure not shown]
1. Early Adenotonsillectomy (eAT) performed by participating ENT surgeons within 1-4 weeks of randomization.
2. Watchful waiting with Supportive Care (WWSC)

Participants in both groups will receive verbal and written information about healthy sleep habits guidance. Participants will be referred for appropriate "usual care" for relevant co-morbidities (for example, poorly controlled asthma, allergies) identified by the study team as needing further optimization of management.

Participants will undergo a standardized assessment of behavior, behavioral performance testing, and other health-related evaluations at baseline and 12 month follow-up time points. At 6 months caregivers will complete neurobehavioral assessments remotely. Virginia will have a 6 month visit in person and repeat baseline assessments. Participants will receive monthly check-in by telephone, , email and/or text messaging in order to maximize retention and to collect additional symptom and HCU reports. Text messaging will only be utilized with families who agree to receive text messages. After 12 months, children who did not get surgery who have a 12-month

PSG showing obstructive sleep apnea (apnea hypopnea index ≥ 3 /hr or obstructive index > 1 /hr) or whose parent reports ongoing symptoms/concerns will be referred back to ENT for further clinical management (such as adenotonsillectomy) as per standard clinical care.

2.2. Study Schema

6-month visit, remote collection of parent behavior assessments at all sites except Virginia

2.3. Blinding and Maintaining the Blind

The study will be single blinded since sham surgery, including use of general anesthesia, would not be ethical, and evidence of tonsillectomy is evident. All members of the Clinical Coordinating Center, research personnel and Steering Committee members, including investigators, quality control personnel, scorers, data entry staff, polysomnologists, and staff performing anthropometry, behavioral testing, and blood pressure, will be blinded to the study arm. Unblinded personnel include the research coordinator who will make the intervention appointments, the otolaryngologist performing the surgery, the research coordinator making monthly contact by telephone, email, and/or text messaging and assessing for adverse events, the study's external Medical Safety Monitor, and selected DCC personnel. The unblinded research coordinator will not be administering any tests or measurements that could be influenced by interview or administration technique. If cases of unblinding are identified, a protocol deviation will be reported.

Each site will designate an unblinded research coordinator/assistant who will have knowledge of the treatment arm assignment. The unblinded research coordinator will be responsible for informing the parent/legal guardian of the treatment arm assignment, making follow-up contact by telephone, , email and/or text messaging, assessing for AE's, scheduling AT within 1-4 weeks for the eAT group, and scheduling WWS re-evaluation after the Month 12 visit.

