2.4.3. Follow-up Contacts

eAT arm only: AT surgery 1-4 weeks from randomization within Month 1

WWS arm only: ENT re-evaluation visit with 1-4 weeks after Endpoint Visit if indicated by 12-month PSG revealing obstructive sleep apnea (AHI ≥ 3.0 /hr. or obstructive apnea index > 1 /hr.) or parent reporting concerning symptoms.

Both groups:

- Monthly contact by telephone, email and/or text messaging , for health care utilization, medication, adverse event inquiries and to support study participation.
- Check In questionnaires and surveys will be completed bi-monthly, at months 2, 4, 6, 8, and 10.
- Interim remote visit at 6 months for caregiver questionnaires and neuro behavioral assessments, adverse event and health care utilization inquiry, and teacher forms of behavior rating scales.
 - Virginia will have in person child neurobehavior testing in addition to assessments above.
- Endpoint Visit at Month 12 for behavioral and performance testing; questionnaires; anthropometry, and BP measures. Behavioral rating scales mailed to teachers.
- Follow-up research PSG at Month 12
- Follow up questionnaires after participation ended to assess feasibility of conducting a study to evaluate long-term outcomes of mild SDB

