9.5. Monthly caregiver interviews

As part of ongoing contact with participants (see Appendix A Visit Schedule), caregivers will be contacted on a bi-monthly basis for completion of check in questionnaires and surveys. Centrally trained research coordinators will administer these questionnaires by telephone, email and/or text messaging at months 2, 4, 6, 8, 10 and in person visit at 12 months. A structured interview that will identify adverse events and HCU, including hospitalizations (reason, place and number of days), emergency room visits (reason, place), unscheduled and scheduled medical outpatient visits, and medication prescriptions. The coordinator will use a script with follow-up questions and record all information in the CRF.

If parents cannot be reached by phone for monthly calls, we will provide parents direct links to The SLICE data management system provided by The DCC. However, adverse

events and healthcare utilization will be followed up by phone calls as there are many nuances that need direct communication with the coordinators.

On alternate months of check in questionnaires, caregivers will be contacted to assess for adverse events and health care utilization only.

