9.6. Health care utilization (HCU) and electronic medical record (EMR) surveillance

EMR will be tracked by both monthly manual review of EMR by the Research Coordinator after each reported adverse event or HCU event, and by automated surveillance of billing records and pharmacy records using query systems co-developed by [name], conducted approximately bi-annually. At each monthly check-in by telephone, email and/or text messaging, or in-person visit, the research coordinator will conduct a structured interview that will identify adverse events and HCU, including hospitalizations (reason, place and number of days), emergency room visits (reason, place), unscheduled and scheduled medical outpatient visits, and medication prescriptions. Data will be entered into a CRF. In addition, each health system's billing system informatics analytics team will extract relevant information from inpatient, outpatient and pharmacy records as outlined in the DCC application. Query results will be returned monthly to the research coordinator who will extract the information to the CRF and compare these data to the parent-reported data. When discrepancies are identified, the research coordinator will attempt to resolve differences by further interviews with the caregiver, requests to other health institutions for medical record release, or by consulting with the DCC. Healthcare utilization data will be collected prospectively through ongoing surveillance of electronic medical records (EMR) for up 24 months following randomization of subjects. We will utilize a query structure to be used by the EMR informatics analytics team for ongoing EMR surveillance for extracting relevant information from inpatient, outpatient and pharmacy records.

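### Health care utilization is collected by the unblinded coordinator's interview, contrary to section 2.3, and no Aim 2 analysis separates the data sources

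*Combined protocol and SAP*

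**What the plan says.** Section 2.3 names among the unblinded personnel "the research coordinator making monthly contact by telephone, email, and/or text messaging and assessing for adverse events". It then says of the unblinded coordinator: "The unblinded research coordinator will not be administering any tests or measurements that could be influenced by interview or administration technique".

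Section 2.4.3 gives the purpose of the monthly contact in both groups: "for health care utilization, medication, adverse event inquiries and to support study participation". Section 9.6 says that at each monthly check-in or in-person visit "the research coordinator will conduct a structured interview that will identify adverse events and HCU", covering hospitalizations, emergency visits, outpatient visits and prescriptions. Section 9.5 adds: "The coordinator will use a script with follow-up questions and record all information in the CRF".

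Records enter by two routes in section 9.6. One is "monthly manual review of EMR by the Research Coordinator after each reported adverse event or HCU event". The other is "automated surveillance of billing records and pharmacy records using query systems". Query results go back to the research coordinator, who enters them in the case report form and compares them with the parent's report. Where they differ, "the research coordinator will attempt to resolve differences by further interviews with the caregiver", or requests records from other institutions, or consults the data coordinating center. Sections 9.7.3 and 9.7.4 describe EMR surveillance at the check-ins and at Month 6 without making it depend on a reported event.

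Section 3.2 lists caregiver report, EMR surveillance, and billing and pharmacy records as sources for HCU. Section 19 (Aim 2) plans rank-sum tests and count models, run with and without events linked to the surgery and its perioperative care.

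**The concern.** The blinding statement does not hold for HCU. A scripted interview with follow-up questions is a measurement that technique can influence, and the person conducting it knows the arm. Families in the surgical arm also have perioperative dealings that could change how much is asked or volunteered about other visits.

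Aim 2 consists entirely of HCU, and similar events define the asthma exacerbation analysis. If events were captured more completely in one arm, part of an observed difference would reflect ascertainment. The plan describes no blinded HCU assessor or adjudicator, and no analysis in Section 19 would show whether the result depends on the interview.

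**Working it through.** **1. Is the interviewer the unblinded coordinator?** Sections 9.5 and 9.6 say only research coordinator. The identification comes from three places:
- Section 2.3 makes the monthly-contact coordinator unblinded.
- Section 2.4.3 puts the HCU inquiry in that contact.
- The interview in sections 9.5 and 9.6 covers adverse events and HCU together, and sections 2.3, 9.9.5 and 10 give adverse event assessment to the unblinded coordinator.

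This covers the ten check-ins in section 9.7.3 (Months 1-5 and 7-11). For Months 6 and 12, sections 9.7.4 and 9.7.6 say study staff, without stating whether they are blinded.

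**2. Which source is free of the interview?**
- Caregiver report: none of it.
- Manual chart review: unclear. Section 9.6 ties it to reported events; sections 9.7.3 and 9.7.4 do not.
- Automated queries: independent when run, but not once the coordinator has transcribed and reconciled them.

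**3. The plan's own figures.** Evaluable sample: 460 × (1 − 0.20) = 368, or 184 per arm, as stated. Two-sided 5% Wilcoxon rank-sum test on the plan's Poisson rates, 2,000 samples per case:
- Hospitalizations, 0.06 vs 0.25 per child-year: power 99.75% (plan: above 99%).
- Specialist consultations, 1.9 vs 3.5: about 100% (plan: above 99%).
- Emergency visits, 0.35 vs 0.37: about 6%, consistent with the limited power the plan concedes.

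The power figures are reproduced. They take capture to be equal in the two arms.

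**4. What unequal capture would do.** The documents give no capture rate, so the ratio s of capture in one arm to capture in the other is an assumption. The true rate is set equal in both arms (the plan's untreated rate) and one arm's recorded rate is multiplied by s. The apparent rate ratio is 1/s: 1/0.95 = 1.05 and 1/0.90 = 1.11. Chance of a significant result at nominal 5%, 184 per arm, 4,000 samples per point:

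| s | Consultations (3.5/yr) | Emergency visits (0.37/yr) | Hospitalizations (0.25/yr) |
|---|---|---|---|
| 1.00 | 5% | 5% | 5% |
| 0.95 | 14% | 6% | 5% |
| 0.90 | 44% | 8% | 8% |
| 0.80 | 96% | 22% | 16% |

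Hand check for consultations at s = 0.90: the difference is 3.5 × 0.10 = 0.35, its standard error is √((3.5 + 3.15)/184) = 0.190, and z = 0.35/0.190 = 1.84. The chance of exceeding 1.96 is then about 45%, which agrees with the simulation.

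Consultations stand in here for frequent outpatient events generally. Section 19 expects skewed, possibly overdispersed counts. Extra variance would lower these percentages at the same s.

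**The case against.** The strongest reply is that several safeguards already exist. The interview is scripted and coordinators are centrally trained. Parent report is checked against billing and pharmacy queries. Section 19 already repeats the Aim 2 analyses without perioperative events, which removes the most obvious asymmetry between arms. Caregivers know the arm, so a blinded interviewer would not remove reporting bias. Secondary analyses are exploratory, and section 9.2.7 assigns performance testing to a blinded coordinator. All of this stands, and it limits the consequence. It does not make the sentence in section 2.3 true, and excluding perioperative events does not address differential probing about unrelated visits.

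Three stronger readings are tempting and are not supported:
- *Chart review merely inherits what the interview found.* Sections 9.7.3 and 9.7.4 describe EMR surveillance without a reported-event condition, so the documents conflict on this and do not settle it.
- *The automated queries are an arm-neutral source as they stand.* Their results reach the case report form through the research coordinator. In-system care could itself differ by arm once one arm has had surgery at the site.
- *A capture gap of this kind would rival the planned effects.* The plan's assumed ratios are 0.06/0.25 = 0.24 for hospitalizations and 1.9/3.5 = 0.54 for consultations, far from 1.05-1.11. Only emergency visits (0.35/0.37 = 0.95) are of that order, and the plan concedes little power there.

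The protocol also refers statistical and HCU extraction details to a data coordinating center application that is not among these documents. A by-source analysis could be described there; Section 19 contains none.

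**Conclusion.** The contradiction is confirmed on the text, and HCU ascertainment for Aim 2 is not blinded. A reader might infer that the Aim 2 comparison is biased by a known amount or toward surgery. The documents support neither: fuller capture in the surgical arm would work against a utilization benefit, and fuller capture under watchful waiting would work toward one.

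Under assumed capture differences of 5-10%, Poisson counts and 184 per arm, the false-positive rate rises materially only for frequent outpatient events (about 14-44%). It stays near nominal for hospitalizations and emergency visits (about 5-8%). This is a low-severity point about a secondary, exploratory aim. It is worth acting on because no analysis in Section 19 tests the dependence and a test would be cheap.

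**What to change.** 1. Correct the sentence in section 2.3 so that it excepts the HCU interview, and reconcile it with sections 2.4.3, 9.5, 9.6, 9.7.3 and 9.7.4. State who conducts the Month 6 and Month 12 inquiries, whether that person is blinded, and whether manual EMR review follows a schedule for everyone or only reported events.
2. Retain the automated billing and pharmacy query output, or a source flag on each event, as it stood before coordinator reconciliation.
3. Prespecify an Aim 2 sensitivity analysis on query-identified events only, with the same definition in both arms, with and without perioperative events, reported beside the combined count.

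Cost: the queries are already planned, so this needs a text correction, retention of the raw output or a flag, and one further analysis. The documents do not say whether the raw output is kept, so that should be confirmed first. The downside is that a query-only count misses care outside the site's health system, and that loss could differ by arm. It is therefore supportive and does not replace the main count.

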2.4. Overview of Study Design

See Appendix A for a summary of study visits and all study related procedures

2.4.1. Screening Visit

Screening of ENT, sleep clinic, general pediatric or other internal clinical practice patients (including electronic medical records [EMR] and existing PSG review) will be performed to identify potentially eligible participants to ascertain preliminary study eligibility. Outside referring physicians will be contacted for permission to approach external practice patients. All HIPAA requirements will be met.

- Obtain informed consent and confirm further eligibility criteria with parent interview (at face-to-face encounter).
- Refer for ENT evaluation (if not done within 3 months of randomization) to confirm surgical candidacy.
- Arrange a research baseline PSG with central scoring. (If a standardized clinical PSG is available, this will be obtained and centrally scored to confirm final eligibility criteria.)
- Perform the ABAS-III if possible (if time does not permit, this will be performed at the baseline visit).

2.4.2. Baseline Visit

- Perform baseline assessments and procedures: behavioral and performance testing and questionnaires including the parent-completed BRIEF2/P; weight, height, anthropometry, and blood pressure measures; lab tests (serum IgE, urinary cotinine); provide healthy sleep guidance; ; mail teacher behavioral rating scales. To ensure that at least one of the primary co-outcomes is available, the parent version of the BRIEF2/P must be completed before a participant can be randomized.
- Randomize to eAT versus WWS

2.4.3. Follow-up Contacts

eAT arm only: AT surgery 1-4 weeks from randomization within Month 1

WWS arm only: ENT re-evaluation visit with 1-4 weeks after Endpoint Visit if indicated by 12-month PSG revealing obstructive sleep apnea (AHI ≥ 3.0 /hr. or obstructive apnea index > 1 /hr.) or parent reporting concerning symptoms.

Both groups:

- Monthly contact by telephone, email and/or text messaging , for health care utilization, medication, adverse event inquiries and to support study participation.
- Check In questionnaires and surveys will be completed bi-monthly, at months 2, 4, 6, 8, and 10.
- Interim remote visit at 6 months for caregiver questionnaires and neuro behavioral assessments, adverse event and health care utilization inquiry, and teacher forms of behavior rating scales.
 - Virginia will have in person child neurobehavior testing in addition to assessments above.
- Endpoint Visit at Month 12 for behavioral and performance testing; questionnaires; anthropometry, and BP measures. Behavioral rating scales mailed to teachers.
- Follow-up research PSG at Month 12
- Follow up questionnaires after participation ended to assess feasibility of conducting a study to evaluate long-term outcomes of mild SDB

- External Medical Safety Monitor ([name], University of Rochester) will provide safety monitoring and central adjudication of treatment failures and serious and unexpected adverse events. Although all sites are responsible for local reporting of AEs, the Independent Medical Monitor will be responsible for adjudicating the status of potential Treatment Failures as used as a study outcome.
- The NHLBI has established an external DSMB according to NHLBI policies. Members include experts in sleep medicine, biostatistics, pediatrics, neurocognition, surgery, and ethics (some overlapping). The DSMB has convened to review the final protocol and DSMB Charter before study initiation and will continue to meet periodically, and not less frequently than annually. The DSMB Chair and the Independent Medical Monitor will receive all reports of serious adverse and unexpected adverse events and treatment failures in real time. The DSMB has requested to receive interim reports on a quarterly basis sent electronically to all DSMB members. The DCC Project Manager is responsible for assembling materials/reports for the DSMB and NIH and maintaining all regulatory files across the duration of the study.
- The study will be governed by a Steering Committee composed of each PI, and leaders of the Quality Control subcommittees.
- Steering Committee subcommittees will be charged with tasks associated with specific operations and quality control activities and will include Protocol Development, Protocol Operations, Surgical Quality Control, Neurobehavioral Quality Control, Recruitment & Retention, and Publications & Presentations. An external Data Safety and Monitoring Board will be established by NHLBI.

3. Study Endpoints

